10.1 Adverse Event Characteristics

CTCAE term (AE description) and grade: The descriptions and grading scales found in the revised NCI Common Terminology Criteria for Adverse Events (CTCAE) version 5.0 will be utilized for AE reporting. All appropriate treatment areas should have access to a copy of the CTCAE version 5.0. A copy of the CTCAE version 5.0 can be downloaded from the CTEP web site:
[REDACTED])

- a. Adverse event monitoring and reporting is a routine part of every clinical trial.
- b. Identify the grade and severity of the event using the CTCAE version 5.0.
- c. Determine whether the event is expected or unexpected (see Section 10.2).
- d. Determine if the adverse event is related to the study intervention (agent, treatment or procedure) (see Section 10.3).
- e. Determine whether the event must be reported as an expedited report. If yes, determine the timeframe/mechanism (see Section 10.4).
- f. Determine if other reporting is required (see Section 10.5).
- g. Note: All AEs reported via expedited mechanisms must also be reported via the routine data reporting mechanisms defined by the protocol (see Section 18.0).

Each CTCAE term in the current version is a unique representation of a specific event used for medical documentation and scientific analysis and is a single MedDRA Lowest Level Term (LLT).

NOTE: A severe AE, as defined by the above grading scale, is NOT the same as serious AE which is defined in the table in Section 10.4.

10.2 Expected vs. Unexpected Events

Expected events - are those described within the Section 15.0 of the protocol, the study specific consent form, package insert (if applicable), and/or the investigator brochure, (if an investigator brochure is not required, otherwise described in the general investigational plan).

Unexpected adverse events or suspected adverse reactions are those not listed in Section 15.0 of the protocol, the study specific consent form, package insert (if applicable), or in the investigator brochure (or are not listed at the specificity or severity that has been observed); if an investigator brochure is not required or available, is not consistent with the risk information described in the general investigational plan.

Unexpected also refers to adverse events or suspected adverse reactions that are mentioned in the investigator brochure as occurring with a class of drugs but have not been observed with the drug under investigation.

10.3 Assessment of Attribution

When assessing whether an adverse event is related to a medical treatment or procedure, the following attribution categories are utilized:

- Definite - The adverse event is *clearly related* to the agent(s).
- Probable - The adverse event is *likely related* to the agent(s).
- Possible - The adverse event *may be related* to the agent(s).
- Unlikely - The adverse event is *doubtfully related* to the agent(s).
- Unrelated - The adverse event is *clearly NOT related* to the agent(s).

Events determined to be possibly, probably or definitely attributed to a medical treatment suggest there is evidence to indicate a causal relationship between the drug/device and the adverse event.

Assessment of Causality

The investigator is obligated to assess the relationship between investigational product, protocol-required therapies or study-mandated procedure and each occurrence of each adverse event/serious adverse event.

Relatedness means that there are facts or reasons to support a relationship between investigational product and the event.

The investigator will use clinical judgment to determine the relationship.

Alternative causes, such as underlying disease(s), concomitant therapy, and other risk factors, as well as the temporal relationship of the event to study treatment administration will be considered and investigated.

The investigator will also consult the Investigator's Brochure and/or Product Information, for marketed products, in his/her assessment.

For each adverse event/serious adverse event, the investigator must document in the medical notes that he/she has reviewed the adverse event/serious adverse event and has provided an assessment of causality.

There may be situations in which a serious adverse event has occurred and the

investigator has minimal information to include in the initial report. However, it is very important that the investigator always make an assessment of causality for every event before the initial transmission of the serious adverse event data.

The investigator may change his/her opinion of causality in light of follow-up information and send a serious adverse event follow-up report with the updated causality assessment.

The causality assessment is 1 of the criteria used when determining regulatory reporting requirements.

Follow-up of Adverse Event and Serious Adverse Event

The investigator is obligated to perform or arrange for the conduct of supplemental measurements and/or evaluations as medically indicated to elucidate the nature and/or causality of the adverse event or serious adverse event as fully as possible. This may include additional laboratory tests or investigations, histopathological examinations, or consultation with other health care professionals.

If a subject is permanently withdrawn from protocol-required therapies because of a serious adverse event, this information must be recorded.

If a subject dies during participation in the study or during a recognized follow-up period as defined in Section 13.0, the investigator will provide a copy of any postmortem findings including histopathology.

New or updated information will be recorded in the originally completed Event CRF.

The investigator will submit any updated serious adverse event data within reporting timeline.

10.31 Special Situations for Expedited Reporting

Exceptions to Expedited Reporting: EXPECTED Serious Adverse Events

An expedited report may not be required for specific Grade 1, 2 and 3 Serious Adverse Events where the AE is **EXPECTED**. Any protocol specific reporting procedures **MUST BE SPECIFIED BELOW** and will supersede the standard Expedited Adverse Event Reporting Requirements:

Note: These exceptions only apply if the adverse event does not result in hospitalization, immediately life-threatening or resulted in persistent/significant disability or death.

If the adverse event results in hospitalization, immediately life-threatening or resulted in persistent/significant disability or death, then the standard expedited adverse events reporting requirements must be followed.

System Organ Class (SOC)	Adverse event/Symptoms	CTCAE Grade at which the event will not be expeditiously reported.
Gastrointestinal Disorders	Diarrhea	Any Grade
	Dyspepsia	
	Nausea	
	Vomiting	Grades 1-3
	Colitis	
	Pancreatitis	
General disorders and administrations site conditions	Anorexia	Any Grade
	Asthenia	
	Dehydration	
	Fatigue	
	Malaise	
	Weight loss	
Hepatobiliary disorders	Cholecystitis	Grades 1-3
Infections and infestations	Lung Infection	Grades 1-3
	Sinusitis	
	Skin infection	
	Urinary tract infection	
Investigations	Alkaline phosphatase increased	Any Grade
	Alanine aminotransferase increased	
	Aspartate aminotransferase increased	
	Lymphocyte count decreased	
Metabolism and nutrition disorders	Hyperkalemia	Any Grade
	Hypocalcemia	
	Hypomagnesemia	
	Hyponatremia	
Musculoskeletal and connective tissue disorders	Arthralgia	Any Grade
	Back pain	
	Musculoskeletal and connective tissue disorder – Other (muscle spasms)	
	Alopecia	
Skin and subcutaneous tissue disorders	Rash acneiform	Any Grade
	Rash maculo-papular	
	Palmar-plantar erythrodysesthesia syndrome	

10.311 Death

- Any death occurring within 30 days of the last dose, regardless of attribution to an agent/intervention under an IND/IDE requires expedited reporting within 24-hours.

- Any death occurring greater than 30 days with an attribution of possible, probable, or definite to an agent/intervention under an IND/IDE requires expedited reporting within 24-hours.
- Reportable categories of Death
 - Death attributable to a CTCAE term.
 - Death Neonatal: A disorder characterized by cessation of life during the first 28 days of life.
 - Death NOS: A cessation of life that cannot be attributed to a CTCAE term associated with Grade 5.
 - Sudden death NOS: A sudden (defined as instant or within one hour of the onset of symptoms) or an unobserved cessation of life that cannot be attributed to a CTCAE term associated with Grade 5.
 - Death due to progressive disease that cannot be attributed to a CTCAE term associated with Grade 5 should be reported as **Grade 5 “Disease progression”** under the system organ class (SOC) of General Disorders and Administration Site Conditions. Evidence that the death was a manifestation of underlying disease (e.g., radiological changes suggesting tumor growth or progression; clinical deterioration associated with a disease process) should be submitted.

10.312 Secondary Malignancy

- A **secondary malignancy** is a cancer caused by treatment for a previous malignancy (e.g., treatment with investigational agent/intervention, radiation or chemotherapy). A secondary malignancy is not considered a metastasis of the initial neoplasm.
- All secondary malignancies that occur following treatment with an agent under an IND/IDE to be reported. Three options are available to describe the event:
 - Leukemia secondary to oncology chemotherapy (e.g., Acute Myelocytic Leukemia [AML])

- Myelodysplastic syndrome (MDS)
- Treatment-related secondary malignancy
- Any malignancy possibly related to cancer treatment (including AML/MDS) should also be reported via the routine reporting mechanisms outlined in each protocol.

10.313 Second Malignancy

- A second malignancy is one unrelated to the treatment of a prior malignancy (and is NOT a metastasis from the initial malignancy). Second malignancies require ONLY routine reporting.

10.314 Pregnancy

The investigator should report all pregnancies, including those of partners of male patients, within 24 hours to ACCRU by submitting the Pregnancy Notification Worksheet located on the ACCRU website under Manuals and Forms. The funding sponsor will be notified by ACCRU within 10 calendar days. The sponsor may ask for follow up evaluation of the pregnancy, fetus, and child.

Prior to obtaining private information about a pregnant woman and her infant, the investigator must obtain consent from the pregnant woman and the newborn infant's parent or legal guardian before any data collection can occur. A consent form will need to be submitted to the IRB for these subjects if a pregnancy occurs. If informed consent is not obtained, no information may be collected.

In cases of fetal death, miscarriage or abortion the mother is the patient. In cases where the child/fetus experiences a serious adverse event other than fetal death, the child/fetus is the patient.

NOTE: When submitting ACCRU Adverse Event Report reports for "Pregnancy", "Pregnancy loss", or "Neonatal loss", the potential risk of exposure of the fetus to the investigational agent(s) or chemotherapy agent(s) should be documented in the "Description of Event" section. Include any available medical documentation.

10.4 Expedited Reporting Requirements for Studies using Commercial Agent(s) ONLY:

Expedited Reporting Requirements for Adverse Events that Occur in a Non-IND/IDE trial within 30 Days of the Last Administration of a Commercial Agent^{1,2}

FDA REPORTING REQUIREMENTS FOR SERIOUS ADVERSE EVENTS (21 CFR Part 312)

NOTE: Investigators **MUST** immediately report to the sponsor **ANY** Serious Adverse Events, whether or not they are considered related to the investigational agent(s)/intervention (21 CFR 312.64)

An adverse event is considered serious if it results in **ANY** of the following outcomes:

- 1) Death
- 2) A life-threatening adverse event
- 3) An adverse event that results in inpatient hospitalization or prolongation of existing hospitalization for \geq 24 hours
- 4) A persistent or significant incapacity or substantial disruption of the ability to conduct normal life functions
- 5) A congenital anomaly/birth defect.
- 6) Important Medical Events (IME) that may not result in death, be life threatening, or require hospitalization may be considered serious when, based upon medical judgment, they may jeopardize the patient or subject and may require medical or surgical intervention to prevent one of the outcomes listed in this definition. (FDA, 21 CFR 312.32; ICH E2A and ICH E6).

ALL SERIOUS adverse events that meet the above criteria **MUST** be immediately reported to the sponsor within the timeframes detailed in the table below.

Hospitalization	Grade 1 Timeframes	Grade 2 Timeframes	Grade 3 Timeframes	Grade 4 & 5 Timeframes
Resulting in Hospitalization \geq 24 hrs		7 Calendar Days		24-Hour; 3 Calendar Days
Not resulting in Hospitalization \geq 24 hrs	Not required		7 Calendar Days	

Expedited AE reporting timelines are defined as:

- “24-Hour; 3 Calendar Days” - The AE must initially be reported within 24 hours of learning of the AE, followed by a complete expedited report within 3 calendar days of the initial 24-hour report.
- “7 Calendar Days” - A complete expedited report on the AE must be submitted within 7 calendar days of learning of the AE.

¹Serious adverse events that occur more than 30 days after the last administration of investigational agent/intervention and have an attribution of possible, probable, or definite require reporting as follows:

Expedited 24-hour notification followed by complete report within 3 calendar days for:

- All Grade 4, and Grade 5 AEs

Expedited 7 calendar day reports for:

- Grade 2 adverse events resulting in hospitalization or prolongation of hospitalization
- Grade 3 adverse events

² For studies using PET or SPECT IND agents, the AE reporting period is limited to 10 radioactive half-lives, rounded UP to the nearest whole day, after the agent/intervention was last administered. Footnote “1” above applies after this reporting period.

Effective Date: May 5, 2011

Follow site-specific reporting guidelines.

Commercial agent expedited reports must be submitted to the FDA via MedWatch.3500A

Instructions for completing the MedWatch 3500A:

Submit copies along with the ACCRU MedWatch Cover Sheet found on the ACCRU Website to the ACCRU SAE Coordinator via fax [REDACTED] The ACCRU SAE Coordinator will forward to the funding sponsor via fax [REDACTED]

The ACCRU SAE Coordinator will forward to [REDACTED] as appropriate. The ACCRU IND Coordinator will assist the sponsor-investigator in notifying the FDA if required.

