10.52 Baseline and Adverse Events Evaluations

The following pre-treatment symptoms/conditions are to be graded at baseline and adverse events are to be graded at each evaluation using CTCAE v5.0 grading.

System Organ Class (SOC)	Adverse event/Symptoms	Baseline	Each Evaluation
General disorders and administration site conditions	Fatigue	X	X
Gastrointestinal disorders	Diarrhea	X	X
Skin and subcutaneous tissue disorders	Rash acneiform	X	X

10.53 **Case Report Forms** - Academic and Community Cancer Research United (ACCRU)

Submit the following AEs not specified in Section 10.5

10.531 Grade 2 AEs deemed *possibly, probably, or definitely* related to the study treatment or procedure.

10.532 Grade 3 and 4 AEs regardless of attribution to the study treatment or procedure.

10.533 Grade 5 AEs (Deaths)

10.5331 Any death within 30 days of the patient's last study treatment or procedure regardless of attribution to the study treatment or procedure.

10.5332 Any death more than 30 days after the patient's last study treatment or procedure that is felt to be at least possibly treatment related must also be submitted as a Grade 5 AE, with a CTCAE type and attribution assigned.

10.54 Late occurring adverse events are any adverse events that occur during Survival Follow-Up reporting periods. These are reported in compliance with Section 4.0 and Section 18.

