16.54 Adverse Events

All eligible patients who have initiated treatment will be considered evaluable for adverse event analyses. The maximum grade for each type of adverse event will be recorded for each patient, and frequency tables will be reviewed to determine adverse event patterns. The overall adverse event rates for grade 3 or higher adverse events will be compared using Chi-Square or Fisher's Exact tests.

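### Read literally, Section 16.54 counts Grade 5 'Disease progression' deaths in the between-arm grade 3 or higher adverse event comparison, mixing disease outcome with tolerability (minor)

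*Combined protocol and SAP*

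**What the plan says.** Four places bear on this.

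- **Coding (10.311).** "Death due to progressive disease that cannot be attributed to a CTCAE term associated with Grade 5 should be reported as"; the label then given is Grade 5 'Disease progression', filed with the general disorders. This is a residual code: it applies only when no other CTCAE term with a Grade 5 fits the death.
- **Collection (10.53).** Under the heading for Grade 5 adverse events, 10.5331 asks for "Any death within 30 days of the patient's last study treatment or procedure regardless of attribution to the study treatment or procedure". For lower grades, 10.532 asks for "Grade 3 and 4 AEs regardless of attribution to the study treatment or procedure".
- **Link between reporting routes (10.1).** "All AEs reported via expedited mechanisms must also be reported via the routine data reporting mechanisms defined by the protocol".
- **Analysis (16.54).** Among eligible patients who started treatment, "The overall adverse event rates for grade 3 or higher adverse events will be compared" by a chi-square or Fisher's exact test. Maximum grade per type of event is also recorded and reviewed in frequency tables.

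Section 16.5 makes all secondary p-values descriptive. Goal 2.24 is to compare the safety and tolerability of the two arms.

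**The concern.** Grade 5 is a grade 3 or higher event. If a progression death carries an adverse event grade and enters the adverse event data without regard to attribution, an analysis of all grade 3 or higher events picks it up unless told not to. Section 16.54 gives no such instruction.

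The trial is designed on the hypothesis that the arms differ in survival (median 6.5 versus 10 months, 16.15). A safety summary that contains disease deaths can therefore differ between arms because the disease behaved differently, with no difference in what patients tolerated. It can also dilute a real difference in toxicity. At stake is the reading of the headline safety contrast, not the trial's go/no-go decision.

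**Working it through.** **Following the text.**

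1. A residual progressive-disease death becomes Grade 5 'Disease progression' (10.311).
2. If it falls within 30 days of last treatment it goes on the case report form whatever its attribution (10.5331). After 30 days it goes there only if felt to be at least possibly treatment-related (10.5332).
3. The grade 3 or higher comparison in 16.54 has no attribution condition and names no excluded term.
4. The suspension rule in 16.4.2 does have an attribution condition: it counts only grade 4 or higher events at least possibly related to treatment. The plan filters on attribution there and not in 16.54.
5. The Section 10.0 wording that sets aside findings related to progression of the underlying disease concerns abnormal laboratory results and other safety assessments. It does not remove deaths.

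So inclusion follows from unrestricted wording; no sentence includes or excludes the term expressly.

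**Size.** The documents give no expected grade 3 or higher rate for either arm and no expected number of progression deaths in the window, so there is no stated figure to reproduce. What follows is illustration.

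Let b be the grade 3 or higher rate without the progression term and d the share of patients with a coded progression death. If the two are independent, the reported rate is b + (1 − b) × d.

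*No true toxicity difference.* Assume b is equal in both arms at 20% to 60%, and d (standard versus panitumumab) runs from 5% versus 2% up to 19.2% versus 12.9%. The top pair is the proportion dead 2 months after randomization under the plan's medians, 1 − 2^(−2/6.5) and 1 − 2^(−2/10), used only as a rough scale. The extremes of the apparent difference are:

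- b = 60%, d = 5% versus 2%: 62.0% versus 60.8%, a gap of 1.2 points (53 × 0.012 = 0.6 patients per arm).
- b = 20%, d = 15% versus 8%: 32.0% versus 26.4%, a gap of 5.6 points (53 × 0.056 = 3.0 patients per arm).

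With 53 per arm, the chance that this alone gives a two-sided p below 0.05 is about 3% to 9%, close to nominal.

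*A true 10-point excess on panitumumab (assumed).*

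- 40% versus 50%, d = 10% versus 5%: 46.0% versus 52.5%, so 10 points shows as 6.5.
- 30% versus 40%, d = 15% versus 8%: 40.5% versus 44.8%, so 10 points shows as 4.3.
- With d equal in both arms the gap shrinks to (1 − d) × 10; at d = 10% that is 9 points.

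*Direction.* The scenarios above assume more coded deaths on standard therapy. That is not given. The window is time on treatment plus 30 days (8.0, 10.5331), and treatment runs to progression or 24 cycles (Schema, 13.1), so an effective arm is watched for longer. As a rough check, take median PFS as time on treatment: 1.9 months for standard therapy (16.1) and, by assumption, 3.4 to 4.0 months for panitumumab, borrowed from the single-arm cetuximab/irinotecan rechallenge study in 1.3. Add 0.99 months (30/30.44) and use constant hazards:

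- Standard: 1 − exp(−ln2/6.5 × 2.89) = 26.5%.
- Panitumumab: 1 − exp(−ln2/10 × 4.39) = 26.2%, or 1 − exp(−ln2/10 × 4.99) = 29.2%.

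These treat every death in the window as a coded progression death, so they overstate d. At b = 20% the apparent gap is 0.8 × (26.5 − 26.2) = 0.2 points one way, or 0.8 × (29.2 − 26.5) = 2.2 points the other.

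**The case against.** The strongest reply is that Section 10 sets reporting duties while 16.54 is a brief analysis summary, so the plan has left a detail unstated rather than chosen to count these deaths. That is fair as to certainty, and the point is accordingly put as a literal reading. It does not remove the need for a sentence, because nothing else in the documents supplies the exclusion.

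The 24-hour death rule in 10.311 refers to agents under an IND/IDE, while 15.0 calls the study IND exempt. This does not help: 10.5331 captures the same deaths without that condition.

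The per-type frequency tables would show 'Disease progression' on its own row. True, but a reader cannot subtract that row from an any-event rate without knowing which of those patients also had another grade 3 or higher event.

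All-cause reporting is defensible here. Investigators know whether a patient is on an infusion or on tablets (7.1), so attribution is open to bias. This stands, and is why the all-cause comparison should stay as the main one.

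A reader might go further and infer that effective panitumumab would make standard therapy look more toxic, and size this by applying the OS medians to a bare 30 days: 1 − exp(−ln2/6.5 × 30/30.44) = 10.0% versus 1 − exp(−ln2/10 × 30/30.44) = 6.6%, a gap of 3.4 points. The documents do not support that. The window is not 30 days but treatment time plus 30 days; over that window the same method gives no gap or a reversed one. Nor is 3.4 points a bound: the hazard may be higher just after progression, while the residual coding rule and overlap with other severe events pull the figure down.

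**Conclusion.** The point holds in a limited form and is minor. As written, residual progression deaths within 30 days of last treatment fall inside the grade 3 or higher comparison, so that comparison is not purely one of tolerability.

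The effect is probably a few percentage points or less. That judgement rests on assumed rates, independence between other severe events and progression deaths, and constant hazards; none of these can be checked from the documents. Direction depends on time on treatment in each arm, deaths in the full window, and overlap with other grade 3 or higher events, and cannot be stated in advance.

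No decision turns on it. The comparison is secondary with descriptive p-values, the suspension rule counts only events at least possibly related to treatment, and the OS design and analyses are untouched. The harm is to the estimate and how it is read.

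**What to change.** Add to 16.54:

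1. The between-arm comparison of all-cause grade 3 or higher events excludes the term Grade 5 'Disease progression'. Patients with any other grade 3 or higher event, including any other Grade 5 term, still count.
2. Grade 5 'Disease progression' is tabulated separately by arm.
3. A supportive comparison is given for grade 3 or higher events at least possibly related to treatment, with a note that attribution is made by investigators who know the assigned treatment.

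The cost is two or three sentences and one or two tables. The coded term and the attribution categories (10.3) already exist, so data collection and expedited death reporting do not change. The fix does not adjust for arms being observed for different lengths of time; it only removes the disease-death term from the contrast.
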